8.7 Documenting Adverse Events

When an AE or SAE is recorded, the preferred medical terminology or concept should be used. Abbreviations and colloquialisms (eg, jargon or slang) should be avoided.

All AEs (including SAEs) should be recorded on the AE eCRF, and the check box for “Serious” should be ticked for entries that fit the criteria for SAEs. The investigator should also complete an SAE report and submit this to the Sponsor or its designee within 24 hours of knowledge of the event.

Only 1 medical concept should be recorded in the event field on the eCRF.

8.7.1 Diagnosis versus Symptoms and Signs

If known, a diagnosis should be recorded on the eCRF rather than individual signs and symptoms (eg, hepatic failure should be recorded instead of jaundice, asterixis, and elevated transaminases). However, if a constellation of signs and/or symptoms cannot be medically characterized as a single diagnosis or syndrome at the time of reporting, each individual event should be recorded as an AE or SAE on the eCRF. If a diagnosis is subsequently established, it should be reported as follow-up information.

8.7.2 Adverse Event Occurring Secondary to Other Events

In general, AEs occurring secondary to other events (eg, cascade events or clinical sequelae) should be identified by their primary cause with the exception of severe or serious secondary events. For example, if severe diarrhea is known to have resulted in dehydration, it is sufficient to record only diarrhea as an AE or SAE on the eCRF if the dehydration is mild.

However, medically significant AEs occurring secondary to an initiating event that are separated in time should be recorded as independent events on the eCRF. For example, if a severe gastrointestinal hemorrhage leads to renal failure, both events should be recorded separately on the eCRF.

8.7.3 Persistent or Recurrent Adverse Events

A persistent AE is one that extends continuously, without resolution between subject evaluation time points. Such events should only be recorded once in the eCRF unless the severity changes. If a persistent AE becomes more or less severe, it should be recorded again in a new eCRF entry. Please refer to the eCRF Completion Guidelines for information on completing each eCRF.

A recurrent AE is one that occurs and resolves between subject evaluation time points and subsequently recurs. All recurrent AEs should be recorded on the eCRF.

8.7.4 Abnormal Laboratory Values or Abnormal Vital Signs

Not every laboratory abnormality/abnormal vital sign qualifies as an AE. A laboratory test result/abnormal vital sign must be reported as an AE if it is a change from baseline and meets any of the following criteria:

- Accompanied by clinical symptoms
- Results in a change in study treatment (eg, dosage modification, treatment interruption, or treatment discontinuation)
- Results in a medical intervention (eg, potassium supplementation for hypokalemia) or a change in concomitant therapy
- Clinically significant in the investigator's judgment

Investigators are responsible for reviewing all laboratory findings and abnormal vital signs and determining whether each abnormality should be reported as an AE.

If the clinically significant laboratory abnormality is a sign of a disease or syndrome (eg, ALP and bilirubin 5× ULN associated with cholecystitis), only the diagnosis (eg, cholecystitis) needs to be recorded on the eCRF.

If the clinically significant laboratory abnormality is not a sign of a disease or syndrome, the abnormality itself should be recorded as an AE or SAE on the eCRF. If the laboratory abnormality can be characterized by a precise clinical term, the clinical term should be recorded as the AE or SAE. For example, an elevated serum potassium level of 7.0 mmol/L should be recorded as “hyperkalemia.”

Observations of the same clinically significant laboratory abnormality from visit to visit should not be repeatedly recorded as AEs or SAEs on the eCRF, unless their severity, seriousness, or etiology changes.

8.7.5 Preexisting Medical Condition

A preexisting medical condition is one that is present at Screening. Such conditions should be recorded on the eCRF as medical history. A preexisting medical condition should be recorded as an AE or SAE only if the frequency, severity, or character of the condition worsens during the study (excluding deterioration of the study disease conditions). When such events are recorded on the eCRF, it is important to convey the concept that the preexisting condition has changed by including applicable descriptors (eg, “more frequent headaches”).

8.7.6 Pregnancy

A female subject must be instructed to stop taking the study drug and immediately inform the investigator if she becomes pregnant during the study. The investigator should report all pregnancies within 24 hours of awareness to the Sponsor (the reporting period for pregnancy continues up to 30 days after completion of the study drug). The investigator should counsel the subject and discuss the risks of continuing with the pregnancy and the possible effects on the fetus. Monitoring of the subject should continue until outcome of the pregnancy. Pregnancies occurring up to 30 days after the completion of the study drug must also be reported to the investigator.

Male subjects must also be instructed to inform the investigator immediately if their partner becomes pregnant during the study or within 100 days after the last dose of study drug. If such an event occurs, it should be reported as described above.

Pregnancy loss of any kind should always be classified as serious AE (as the Sponsor considers these medically significant), recorded on the eCRF, and expeditiously reported to Sponsor.

Any congenital anomaly/birth defect in a child born to a female subject or female partner of a male subject exposed to the study drug should be recorded and reported as an SAE.

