2.3 Benefit/Risk Assessment

2.3.1 Risk Assessment

HMPL-306 is in the early stage of development, and the clinical safety profile has not yet been established, but some potential risks have been observed from nonclinical studies and clinical data from drugs in the same class. Measures for managing these potential risks are as shown in [Table 3](#).

Table 3 Summary of Potential Risks of HMPL-306

Potential Risk of Clinical Significance	Summary of Data/Rationale for Risk	Mitigation Strategy
Gastrointestinal disorders	[REDACTED] was observed in rats with doses up to [REDACTED] mg/kg of HMPL-306. Gastrointestinal diseases such as nausea, vomiting, diarrhea, mucositis, constipation, abdominal pain, etc. occurred in clinical studies of both enasidenib and ivosidenib.	General guidance to be provided in the protocol for dose interruption/reduction/discontinuation in response to AEs.
Embryotoxicity	At the present stage, the study of effect of HMPL-306 on embryo development has not been implemented. Enasidenib and ivosidenib were associated with maternal toxicity and adverse embryo-fetal effects in pregnant rats.	Women who are pregnant (pregnancy test is positive before drug administration) or breastfeeding will be excluded from the study. Male with partners of childbearing potential or female subjects of childbearing potential will be required to use effective contraception

Table 3 Summary of Potential Risks of HMPL-306

Potential Risk of Clinical Significance	Summary of Data/Rationale for Risk	Mitigation Strategy
		methods. Female subjects of childbearing potential will be tested for pregnancy at every cycle.
Non-infectious leukocytosis	Neutrophil count was seen increased by CCI% in animals administered HMPL-306 (CC mg/kg/day), and no abnormalities were observed at the end of the recovery period. Non-infectious leukocytosis occurred in clinical trials of both enasidenib and ivosidenib.	Peripheral white blood cell count will be monitored at baseline and during the study at regular intervals, particularly at least once weekly in the first 2 cycles (28 days/cycle) of the initial drug administration. Afterward, it will be monitored once a cycle.

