Abnormal hepatic function	In the HMPL-306 high-dose (CC mg/kg/day) group in rats, the CCI showed a CCI% increase and CCI showed CCI% increase. In clinical trials of both enasidenib and ivosidenib, AEs of abnormal hepatic function occurred, including elevated liver enzymes and elevated bilirubin.	Liver function will be routinely monitored.
Eye disorders	A total of 3 rats in the medium-dose (CC mg/kg/day) and high-dose (CC mg/kg/day) groups were found to have CCI. Considering that it is a vital functional organ, ophthalmological examination will be added to the clinical trials.	Ophthalmologic examinations will be performed during the Screening. If the subject has undergone the relevant examinations 60 days before treatment, they will not be required to repeat the test for Screening. After the start of treatment, ocular appearance, and slit lamp examinations will be performed every 3 cycles (ie, Day 1 of Cycles 4, 7, and 10) and during the end of treatment visit. Other ophthalmic examinations will be performed when clinically indicated.
Male reproductive system lesions	In rats given a medium-dose of HMPL-306 (CC mg/kg/day), CCI. In the high-dose (CC mg/kg/day) group, CCI.	Male subjects of childbearing potential will be included only if they agree to use effective contraception methods during the study and within 180 days after the last administration of the study drug.
Pancreatic lesions	CCI was observed in male rats administered with a high-dose of HMPL-306 (CC mg/kg/day) and was not observed during the recovery period.	Serum lipase and amylase will be monitored.
QTcF Interval Prolongation	The inhibitory rate of the negative reference standard and positive reference standard to the hERG potassium current of HMPL-306	QTcF will be monitored throughout the study, and dose modification guidelines are presented for associated AEs based on CTCAE grading criteria.

Table 3 Summary of Potential Risks of HMPL-306

Potential Risk of Clinical Significance	Summary of Data/Rationale for Risk	Mitigation Strategy
	
was within acceptable range (IC_{50} was as high as CCI μM).
 
CCI, QTcF interval prolongation has been seen as a class effect with other approved IDH inhibitors and may be seen with HMPL-306.
	

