13. Female subjects of childbearing potential and male subjects with partners of childbearing potential must agree to use a highly effective form(s) of contraception that results in a low failure rate ($< 1\%$ per year) when used consistently and correctly, starting during the Screening Period, continuing throughout the entire study period, and for 180 days after taking the last dose of study drug. Such methods include oral hormonal contraception (combined estrogen/progestogen or progestogen-only) or highly effective non-oral hormonal contraception (eg, Depo-Provera and Implanon) associated with inhibition of ovulation together with a barrier method (eg, diaphragm, always containing a spermicide), intrauterine device, intrauterine hormone-releasing system, bilateral tubal ligation, vasectomized partner, or sexual abstinence in line with the preferred and usual lifestyle of the subject. Oral and non-oral hormonal contraception should always be combined with an additional contraceptive method (ie, barrier method) because of a potential interaction with the study drug. The same criteria are applicable to male subjects involved in this clinical trial if they have a partner of childbirth potential, and male subjects must always use a condom.

Part 1, Dose Escalation:

14. Subjects must have a documented IDH mutation per immunohistochemistry (IHC), polymerase chain reaction (PCR), or next generation sequencing (NGS) testing of tumor tissue.
15. Subjects must have histologically or cytologically documented, locally advanced or metastatic solid malignancy of any type that has recurred or progressed on available standard treatment and for which no curative therapy exists.
 - a. Subjects with Grade 3 non-enhancing glioma are permitted to enroll to Part 1.

Part 2, Dose Expansion:

16. Subjects in Cohorts A, B, C, C-1, and D must have documented IDH mutation of any of the following subsets: IDH1 (R132), IDH2 (R140), or IDH2 (R172), including any co-mutations, per validated NGS testing of tumor tissue
17. Subjects must have histologically or cytologically documented:
 - b. **Cohort A:** Locally advanced or metastatic cholangiocarcinoma not eligible for curative resection or transplantation. Subjects must have previously received

- ≥1 gemcitabine- or 5-fluorouracil-containing regimen. Subjects must have not progressed on prior IDH treatment unless isoform switching of the IDH mutation has been documented following progression on an IDH inhibitor

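### Contraception is required for 180 days after the last dose, but stated pregnancy reporting stops at 30 days for women and partner notification at 100 days, and the Protocol does not reconcile these periods

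*Protocol*

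**What the plan says.** **Contraception.** Criterion 13 in Protocol Section 5.2 covers both sexes: "Female subjects of childbearing potential and male subjects with partners of childbearing potential must agree to use a highly effective form(s) of contraception". The duty begins in screening, "continuing throughout the entire study period, and for 180 days after taking the last dose of study drug". Table 3 in Section 2.3.1, in the row on male reproductive system lesions, repeats the period for men, who must agree to "use effective contraception methods during the study and within 180 days after the last administration of the study drug".

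**Pregnancy reporting.** Section 8.7.6 gives the 30-day limit for female subjects twice. From investigator to sponsor, "the reporting period for pregnancy continues up to 30 days after completion of the study drug". Towards the investigator, "Pregnancies occurring up to 30 days after the completion of the study drug must also be reported to the investigator". Male subjects must tell the investigator "if their partner becomes pregnant during the study or within 100 days after the last dose of study drug"; such events then follow the procedure set out earlier in the same section.

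**Related rules.** Section 8.2.2 lists pregnancy among events to be reported within 24 hours of the investigator learning of them, and gives no post-dose limit. Section 8.3.5 follows pregnancies arising during the study to outcome. Section 8.7.6 makes pregnancy loss and birth defects serious events without a time limit. Section 8.2.1 keeps only drug-related serious events reportable after the adverse-event period.

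**Background.** The embryotoxicity row of Table 3 states that "the study of effect of HMPL-306 on embryo development has not been implemented" and that two other IDH inhibitors were associated with maternal toxicity and adverse embryo-fetal effects in pregnant rats.

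**The concern.** A contraception period and a pregnancy-reporting period serve linked purposes. If subjects are asked to avoid pregnancy until day 180, a contraceptive failure before day 180 is an event the sponsor would want to hear of. Section 8.7.6 stops well short of that day, by different amounts for the two groups and without a reason. The shorter period applies to the women who took the drug themselves.

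What is at stake is safety information. No embryo-development study of HMPL-306 had been done, so accidental exposures would be an important source of human data. The rules on pregnancy loss and birth defects work reliably only if the site knows of the pregnancy. No efficacy analysis and no primary endpoint is affected.

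**Working it through.** The documents give no calculation of their own to reproduce. The check compares the stated periods, counted in days after the last dose. Completion of study drug and last dose are taken as the same day.

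**Inputs**
- Contraception, both sexes: 180 days (Section 5.2, criterion 13).
- Reporting, female subjects: 30 days (Section 8.7.6).
- Notification, partners of male subjects: 100 days (Section 8.7.6).
- End-of-treatment visit: within 7 (±3) days of the last dose (Section 6.1.19).
- Safety follow-up: 30 (±7) days after that visit (Section 6.1.20). It includes the last scheduled pregnancy test (Section 1.3, Table 1, footnote 13).

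**Share of the contraception period outside the stated rule** = (180 − reporting period) / 180
- Women: (180 − 30) / 180 = 150 / 180 = 83% (days 31 to 180).
- Partners: (180 − 100) / 180 = 80 / 180 = 44% (days 101 to 180).
- Partners, if the 30-day period in the procedure they are referred to also limits reports to the sponsor: 150 / 180 = 83%. This reading conflicts with the explicit 100 days, so it shows an ambiguity and is not a second estimate.

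**Timing of the last scheduled test**
- Nominal, with the end-of-treatment visit on day 7: 7 + 30 = day 37.
- Latest: (7 + 3) + (30 + 7) = day 47.
- Earliest, with the end-of-treatment visit on the day of the last dose: 0 + (30 − 7) = day 23.

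A test that the Protocol itself requires can therefore fall after day 30. If it detects a pregnancy that began after day 30, Section 8.7.6 puts that pregnancy outside the reporting period, while Section 8.2.2 would have it reported within 24 hours.

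**Do other rules extend the period?**
- Section 8.2.2 has no post-dose limit, but its duty starts when the investigator learns of the pregnancy. It does not oblige the subject to tell anyone.
- Section 8.3.5 depends on the pregnancy arising during the study and names no period after dosing.
- Scheduled contact may end early. Efficacy follow-up excludes subjects who stop for progression, and survival follow-up covers only expansion cohorts A, B and D (Section 6.1.20). A Part 1 subject who progresses has no scheduled visit after safety follow-up, apart from any needed to follow unresolved adverse events.

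None of these sets a notification or reporting period of 180 days.

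**The case against.** The strongest reply is that contraception and reporting are different duties, so different lengths are not in themselves a contradiction. That is correct as far as it goes. The Protocol never calls the 180 days a risk window. Table 3 states that figure in the row on male reproductive lesions; its embryotoxicity row gives no duration. What remains is that the lengths are unexplained, that they differ between women and partners, and that Section 8.7.6 does not sit with Section 8.2.2.

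A reader might infer that a pregnancy after day 30 would go unreported and unfollowed. The documents do not support that. Section 8.2.2 is open-ended once the investigator knows. Section 8.3.5 follows pregnancies during the study to outcome. Subjects who stop the drug for reasons other than progression, death, loss to follow-up or withdrawal of consent stay on study with 12-weekly visits, so for them the instruction to report a pregnancy arising during the study can run well past day 30. The rules on pregnancy loss and birth defects have no time limit, and related serious events stay reportable. Later capture is possible, but it depends on circumstance.

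A reader might also infer that most of the period is uncovered for both groups. That holds for women (83%) but not for partners at the stated 100 days (44%).

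Two further limits stand. The percentages count calendar days and do not measure risk: the animal half-lives are redacted and no human half-life is given, so exposure late in the period cannot be judged. And few subjects are concerned: SAP Section 1 says that no patients entered the expansion part, and SAP Section 2.3.1 estimates 27 to 36 in escalation, of whom the rule reaches only those who could become pregnant or whose partners could.

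**Conclusion.** The point holds as a mismatch between sections that needs reconciling. Measured against the 180-day contraception requirement, the stated reporting period omits 150 days (83%) for female subjects, and the stated notification period omits 80 days (44%) for partners of male subjects. It is also unclear whether 30 or 100 days governs partner reports to the sponsor, and whether Section 8.7.6 limits Section 8.2.2. No rule makes notification last as long as the contraception requirement.

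This is worth correcting for a drug with no embryo-development study, but its scope is safety capture in a small population. It does not show that late pregnancies would be missed, and it does not show which of 30, 100 or 180 days is right.

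The conclusion rests on the Amendment 2 text. SAP Section 1 refers to Amendment 3, dated 06 December 2022, which was not supplied and may have changed Section 8.7.6.

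**What to change.** First check whether Amendment 3 already settles this. If not:

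- Reconcile criterion 13 in Section 5.2, Table 3 in Section 2.3.1, Section 8.2.2 and Section 8.7.6. The period for pregnancy notification, reporting and follow-up to outcome should be at least as long as whatever contraception period the Protocol retains, for female subjects and for partners of male subjects alike.
- State one period for partner pregnancies in Section 8.7.6 and drop the reference back to a procedure that carries a different one.
- State that a pregnancy found at the safety follow-up test is reportable whatever day it falls on.
- Tell subjects at the end-of-treatment visit until what date they should notify the site.

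The length of contraception itself is left to the sponsor. The cost is amendment and consent wording and slightly longer pharmacovigilance at sites. Subjects report for themselves, so no visits or tests are added and no dosing rule changes.

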8.7.7 Worsening of Malignancy

Worsening and/or progression of the subject’s malignancy should not be recorded as an AE or SAE. These data will be captured as efficacy assessment data only. If there is any uncertainty about an AE being related only to the disease under study, it should be reported as an AE or SAE.

8.7.8 Death

All deaths that occur during the protocol-specified AE reporting period must have the underlying cause reported to the Sponsor as an SAE, with death listed as the outcome. Deaths due to the progression of disease must also be reported to the Sponsor as an SAE. Death events that occur after 30 days following the last dose of study drug must be reported to the Sponsor as an SAE only

if it is confirmed as related to study drug. If the primary cause of death is unknown and cannot be ascertained at the time of reporting, please record “Unknown cause death” on the eCRF, and the “unexplained/unknown death” should be reported expeditiously as an SAE. The SAE should be reported before the specific cause of death has been determined.

8.7.9 Overdose

For this study, any dose of HMPL-306 greater than the intended dose will be considered an overdose. No specific information is available on the treatment of overdose of HMPL-306. In the event of overdose, further HMPL-306 administration should be held, and the subject should be observed closely for signs of toxicities. Appropriate supportive treatment should also be provided if clinically indicated. In the event of accidental or intentional overdose, the investigator or other site personnel should inform the Sponsor study representatives immediately, or no later than 24 hours.

- An overdose with associated AEs/SAEs should be recorded as the AE diagnosis/symptoms on the relevant AE/SAE modules in the case report form (CRF) and on the study drug CRF module
- An overdose with no associated signs or symptoms should only be reported on the study drug CRF module
- Overdose will not be reported as an AE/SAE unless it is an intentional overdose taken with possible suicidal/self-harming intent. Such overdoses should be reported regardless of sequelae

9 ANALYSIS

9.1 Statistics and Analysis Method

All statistical analyses will be performed under the direction of the Sponsor's personnel. Details of the statistical analysis and data reporting will be provided in the Statistical Analysis Plan (SAP), which will be finalized prior to the database lock.

The timing of analysis for each cohort may be different depending on completion of each cohort, and the final analysis of the study will be conducted at the time of the analysis of the last cohort. No interim analysis is planned for the study. However, the accrued data from any cohort may be analyzed for internal decision-making purposes, for example, to provide information for a potential phase 3 study design.

